#### **2.6.3.2.3 TEAEs by Preferred Term**

Tables of all unsolicited TEAEs will be provided by PT sorted in a descending order starting with the frequency of the combined 1083.2 group (mRNA-1083.2 **CCI**  $\mu$ g, mRNA-1083.2 **CCI**  $\mu$ g, and mRNA-1083.2 **CCI**  $\mu$ g).

#### **2.6.3.2.4 TEAEs by Severity**

The following summary tables of TEAEs will be provided by SOC, PT and the maximum severity or toxicity grade using frequency counts and percentages:

- All unsolicited AEs
- All unsolicited AEs that are treatment-related

Summary tables will also be provided by SOC and PT for unsolicited TEAEs that are treatment-related in each of the above categories.

#### **2.6.3.3. Death**

Total number of deaths due to any cause and time of death from injection (numeric and by time point window) will be summarized in a table. In addition, number of participants with occurrences of Unsolicited TEAE Leading to Death will be summarized by SOC and PT using frequency counts and percentages. A listing of deaths including cause of death, and a listing of unsolicited AEs in participants who died will be provided.

#### **2.6.3.4. Clinical Safety Laboratory Tests**

Safety laboratory tests will consist of white blood cell count, hemoglobin, hematocrit, platelets, AST, ALT, creatinine, alkaline phosphatase, and total bilirubin will be assessed at Screening and Day 8. The Toxicity grading scale for healthy adult and adolescent volunteers enrolled in preventive vaccine clinical trials (DHHS, 2007) available in Appendix E will be used to categorize clinical laboratory test results.

Observed values and changes from baseline to post-baseline visit (at Day 8) for continuous hematology and serum chemistry parameters will be summarized by vaccination group. A toxicity grade shift table of the hematology and chemistry parameters from baseline to post-baseline visit will be provided as well.

Listing containing individual participant clinical laboratory tests measurements data will be provided for hematology and serum chemistry. Additionally, participant with any abnormal post-baseline laboratory tests measurements where toxicity grade (Grade 2 or higher) will be listed separately: if a participant has a laboratory result with Grade 2 or higher abnormality after injection visit, then all results for that participant will be presented in the listing. The values that are outside the reference ranges will be flagged in a data listing.

If multiple values are collected within a post-baseline visit/timepoint, the last assessment will be used in the by-visit summary tables. Unscheduled visits (including early termination) will not be summarized in by-visit summaries of data but may contribute to either baseline or post-baseline worst-case (maximum, minimum, etc.) values when applicable. All values will be listed.

#### **2.6.3.5. Vital Signs**

Vital sign measurements will include systolic and diastolic blood pressure, heart rate, respiratory rate, and body temperature (preferred route is oral) and will be assessed at Screening and Day 1. On the day of study intervention administration, vital sign measurements will be collected once before and at least 60 minutes after study intervention. Vital signs may be collected at other study visits in conjunction with a symptom-directed physical examination.

Following injection, any abnormal vital sign measurement should be assessed by the Investigator to determine if it meets AE reporting criteria per protocol and reported as an AE in EDC, if appropriate.

The Toxicity grading scale for healthy adult and adolescent volunteers enrolled in preventive vaccine clinical (DHHS, 2007) available in Appendix F will be used to categorize vital sign measurements observed during this clinical trial.

Observed values and changes from pre-injection (Baseline) to post-injection (at Day 1, 60 minutes after study intervention) for all vital sign measurements will be summarized by

vaccination group. A toxicity grade shift table of the vital signs from pre-injection to post-injection will be provided as well.

A listing containing individual participant vital sign measurement data will be provided. Additionally, participant with any abnormal post-baseline vital sign measurement where toxicity grade (Grade 3 or higher) will be listed separately: if a participant has a vital sign result with Grade 3 or higher abnormality after injection visit, then all results for that participant will be presented in the listing.

If multiple values are collected within a post-baseline visit/timepoint, the last assessment will be used in the by-visit summary tables. Unscheduled visits (including early termination) will not be summarized in by-visit summaries of data but may contribute to either baseline or post-baseline worst-case (maximum, minimum, etc.) values when applicable.

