### **8.3.4. Vital Signs (Part 1 and Part 2)**

Vital sign measurements will include systolic and diastolic blood pressure, heart rate, respiratory rate, and body temperature (preferred route is oral). The participant will be seated for at least 5 minutes before all measurements are taken. Vital signs will be measured at the timepoints indicated in the SoA ([Table 1](#) and [Table 2](#)). On the day of study intervention administration, vital sign measurements will be collected once before and at least 60 minutes after study intervention. Vital signs may be collected at other study visits in conjunction with a symptom-directed physical examination.

Following injection, any abnormal vital sign measurement should be assessed by the Investigator to determine if it meets AE reporting criteria PP and reported as an AE in EDC, if appropriate. The Investigator will continue to monitor the participant with additional assessments until the vital sign value has reached the reference range, returns to the vital sign value at Baseline, is considered stable, or until the Investigator determines that follow-up is no longer medically necessary.

Participants who are febrile (body temperature  $\geq 38.0^{\circ}\text{C}/100.4^{\circ}\text{F}$ ) before injection on Day 1 should be rescheduled within the relevant window period to receive the injection. Participants

who are afebrile with minor illnesses may be administered study intervention at the discretion of the Investigator.

When procedures overlap and are scheduled to occur at the same timepoint, the order of procedures should be vital sign measurements and then blood collection.

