### **8.3.6.      Clinical Safety Laboratory Tests (Part 1)**

All protocol-required laboratory tests, as defined in [Section 10.2](#), must be conducted in accordance with the laboratory manual and the SoA ([Table 1](#)).

Safety laboratory tests will consist of white blood cell count, hemoglobin, hematocrit, platelets, AST, ALT, creatinine, alkaline phosphatase, and total bilirubin.

Additional blood samples for safety laboratory tests may be taken at the discretion of the Investigator if warranted to ensure participant's safety.

- The Investigator must review the laboratory results, document this review, and record any clinically significant changes occurring during the clinical trial as an AE. The laboratory results must be retained with source documents.
- All Screening laboratory results must be reviewed prior to dosing of any study intervention to ensure that the participant's laboratory values meet all inclusion and exclusion criteria.
- All laboratory tests with values considered clinically significantly abnormal during participation in the clinical trial should be repeated until the values return to normal or Baseline or are no longer considered clinically significant by the Investigator or medical monitor. If clinically significant abnormal values do not return to normal/Baseline within a period of time judged reasonable by the Investigator, the etiology should be identified, and the Sponsor notified.

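### Day 1 vital signs: the last-value rule can put a recovered recheck, not the abnormal reading that prompted it, into the post-injection summaries

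*SAP*

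**What the plan says.** **Schedule.** SAP 2.6.3.5 has one planned post-injection vital-sign reading: on Day 1, "vital sign measurements will be collected once before and at least 60 minutes after study intervention". Safety laboratory tests, in Part 1 only, "will be assessed at Screening and Day 8" (SAP 2.6.3.4), so there is one planned post-baseline draw.

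**Repeats.** For an abnormal vital sign after injection, Protocol 8.3.4 states: "The Investigator will continue to monitor the participant with additional assessments until the vital sign value has reached the reference range". The same sentence gives other stopping points: return to the Baseline value, or the value "is considered stable, or until the Investigator determines that follow-up is no longer medically necessary". For laboratory tests the trigger is narrower. Protocol 8.3.6 covers values judged clinically significant, which "should be repeated until the values return to normal or Baseline or are no longer considered clinically significant".

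**Which value is tabulated.** SAP 2.6.3.5 states: "If multiple values are collected within a post-baseline visit/timepoint, the last assessment will be used in the by-visit summary tables". SAP 2.6.3.4 has the same sentence. Both then keep unscheduled visits out of by-visit summaries, while allowing them to feed worst-case values where applicable. Neither section orders a worst-case table. On graded displays, SAP 2.6.3.5 says: "A toxicity grade shift table of the vital signs from pre-injection to post-injection will be provided as well". It does not say whether that table takes the first, last or worst value.

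**Carry-over.** SAP 3.6.3.4 applies the vital-sign section to Part 2. Part 2 has no safety laboratory section.

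**The concern.** The recheck is not a random second measurement. An abnormal reading triggers it, and two of the four stopping points in Protocol 8.3.4 are forms of recovery. A rule that keeps the last of several readings then tends to keep the recovered one. Compared with taking the worst grade, the last value can only match or understate the abnormality.

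Evaluating safety is a primary objective in both parts, and the shift table is the only aggregate display of graded vital signs that the SAP specifies. If arms differ in short-lived changes in blood pressure or heart rate after injection, that table is where a reader would look. The SAP takes the maximum elsewhere: solicited reactions are shown at their highest grade (2.6.3.1) and unsolicited events at their maximum severity (2.6.3.2).

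**Working it through.** **Step 1: trace each kind of repeat through the rules.**

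| Repeat | Rule that applies | Value in the by-visit table |
|---|---|---|
| Day 1 vital sign, recorded under the same post-injection timepoint | Last assessment (SAP 2.6.3.5) | Recheck |
| Vital sign, recorded as an unscheduled visit | Excluded from by-visit summaries (SAP 2.6.3.5) | Abnormal reading |
| Laboratory redraw within the Day 8 visit (Part 1) | Last assessment (SAP 2.6.3.4) | Redraw |
| Laboratory repeat at a later unscheduled visit (Part 1) | Excluded (SAP 2.6.3.4), and not mapped back because Appendix B windows serve immunogenicity only | Abnormal Day 8 value |

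Only the first and third rows replace the abnormal value. The first is the realistic one: participants stay under observation for at least 60 minutes and can be rechecked before they leave.

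**Step 2: where a replaced value can still be seen.** SAP 2.6.3.5 orders a listing of all vital signs and a separate listing that starts at Grade 3. A masked Grade 1 or 2 value, such as a systolic pressure of 141 to 155 mm Hg (SAP Appendix F), reaches only the full listing unless the investigator reports it as an AE. Fever has its own route: the eDiary records the day's highest temperature (Protocol 8.3.10), and it is tabulated at its highest grade.

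**Step 3: check the formula on the plan's own figures.** Protocol Table 9 gives the chance of seeing at least one participant with an AE, 1 − (1 − p)^n. For n = 40:

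- p = 4%: 1 − 0.96^40 = 80.5%, as stated.
- p = 5%: 1 − 0.95^40 = 87.1%, as stated.

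All eight rows of Protocol Tables 8 and 9 reproduce. They concern AEs, not vital signs, and serve only to check the formula.

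**Step 4: illustrate the masking.** Let p be the true proportion of an arm with a graded abnormality and f the share of those participants whose last same-timepoint value is normal. The documents give neither, so both are assumptions. The chance that the shift table shows at least one abnormal participant is 1 − (1 − p(1 − f))^n. With p = 5%:

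| n per arm | f = 0 | f = 0.25 | f = 0.5 | f = 0.75 | f = 1 |
|---|---|---|---|---|---|
| 40 (Part 2) | 87.1% | 78.3% | 63.7% | 39.5% | 0% |
| 50 (Part 1, Cohort A) | 92.3% | 85.2% | 71.8% | 46.7% | 0% |
| 52 (Part 1, Cohort B) | 93.1% | 86.3% | 73.2% | 48.0% | 0% |

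For example, n = 40 and f = 0.5 gives 1 − 0.975^40 = 63.7%. The f = 0 column is also the result when every recheck is entered as unscheduled.

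**Step 5: the same in counts.** Suppose 4 of 40 have a graded reading. Without masking, the table shows 4/40 = 10% (exact 95% CI 2.8% to 23.7%). If all four are rechecked to normal under the same timepoint, it shows 0/40, with upper limit 1 − 0.025^(1/40) = 8.8%. If two are, it shows 2/40 = 5%.

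**The case against.** The strongest reply is that the effect rests on two things the documents leave open. First, whether a same-day recheck shares the timepoint of the 60-minute reading depends on how the eCRF records it. SAP 2.6.3.5 ties the change summary to 60 minutes after injection, so a later reading might count as unscheduled and replace nothing. Second, the last-value rule is written for by-visit tables, and the shift table is not expressly placed under it. Both points stand, which is why the conclusion is conditional. They do not remove it: the last assessment is the only multiple-value rule given, and a shift table built on a single post-injection timepoint most naturally follows it. If it does not, its input is undefined.

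SAP 2.6.1 lets unscheduled values enter maximum and minimum derivations for safety. That does not settle the matter, because it concerns unscheduled measurements, not same-timepoint repeats, and no table of such values is ordered in 2.6.3.4 or 2.6.3.5.

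A reader might infer more than the documents support:

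- **That sites must re-measure until values are normal.** Stability, or no further medical need, also ends vital-sign follow-up, and the laboratory rule covers only clinically significant values.
- **That Day 8 laboratory abnormalities disappear.** The tests are run centrally, so a repeat would usually be a later, unscheduled draw. Excluding it keeps the abnormal Day 8 value in the table.
- **That abnormalities are hidden.** All values are listed. Abnormal vital signs are assessed for AE reporting, clinically significant laboratory changes are recorded as AEs, and AEs are tabulated by arm.

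**Conclusion.** The point holds for Day 1 vital signs in both parts, on two conditions: that the recheck is recorded under the same post-injection timepoint and, for the shift table, that the table follows the last-value rule. The by-visit change summary needs only the first. What would then be missing from every aggregate table is a transient Grade 1 or 2 abnormality, other than fever, that was not reported as an AE. For laboratory tests the exposure is limited to a redraw recorded within the Day 8 visit in Part 1.

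The size cannot be stated. Anything from no loss to loss of all such abnormalities from the table fits the documents, and the figures above illustrate assumed rates. Vital signs and laboratory values are descriptive here and are not among the listed primary endpoints, and no hypothesis test is affected. Severity: minor.

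**What to change.** - **SAP 2.6.3.5 (and so Part 2):** state that the shift table uses the worst post-injection toxicity grade recorded on Day 1, including repeats and unscheduled values. Take the mean change from the first reading made at the protocol time, at least 60 minutes after injection. How a recheck is recorded then no longer affects either table.
- **SAP 2.6.3.4:** state that the shift table uses the worst grade among values recorded at the Day 8 visit.

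The cost is a few sentences and one derivation flag. Reported abnormality rates will be slightly less favourable. No data collection changes.

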#### **2.6.3.6. Pregnancy Testing**

For participants of childbearing potential, a point-of-care urine pregnancy test will be performed at the Screening Visit and before injection at Day 1. At the discretion of the Investigator, a pregnancy test either via blood or point-of-care urine can be performed at any time. For participants of nonchildbearing potential, the FSH level may be measured at the Screening Visit, as necessary, and at the discretion of the Investigator, to confirm menopausal status.

A listing containing individual participant pregnancy test results will be provided for the pregnancy tests and FSH blood levels.

#### **2.6.3.7. Other Safety Data**

##### **2.6.3.7.1 Safety Telephone Calls**

A safety telephone call is a telephone call made to the participant by trained site personnel. This call will follow a script, which will facilitate the collection of relevant safety information.

A listing containing individual participant safety call information will be provided.

### **2.6.3.7.2 Assessment for Respiratory Viral Infection**

For Part 1, during the clinical trial, participants might experience symptoms consistent with ILI or SARS-CoV-2 infection. All participants will provide nasal swab samples before the injection on Day 1 for assessment of infection with respiratory pathogens, including influenza viruses and SARS-CoV-2, as influenza or COVID-19 symptoms may confound reactogenicity assessments. Throughout the clinical trial, the participant will be instructed to contact the study site if they have symptoms suggestive of ILI or SARS-CoV-2. An unscheduled visit for symptom assessment and nasal swab for viral respiratory pathogens will be conducted within 7 days of the onset of any potential ILI or SARS-CoV-2 symptoms.

The Assessment for Respiratory Viral Infection is available in protocol Section 8.3.7 corresponding to the Efficacy Analysis. A listing presenting for each participants the symptoms of ILI/COVID-19 will be provided as well.

### **2.6.3.7.3 Physical examination**

A complete physical examination will include, at a minimum, assessments of skin, head, ears, eyes, nose, throat, neck, thyroid, lungs, heart, cardiovascular system, abdomen, lymph nodes, and musculoskeletal system and extremities. Height and weight will also be measured and recorded.

### **2.6.3.7.4 Electrocardiograms**

For participants aged  $\geq 18$  to  $< 51$  only, a 12-lead ECG will be obtained at Day 1, after 10 minutes of supine rest. The purpose of the ECG is to serve as a Baseline comparison, should it be necessary, for subsequent clinical evaluation of suspected myocarditis and/or pericarditis. Clinically significant abnormal ECG findings, if incidentally observed by the Investigator, may contribute to Investigator's assessment of eligibility, at his or her discretion.

## **2.6.4. Immunogenicity Analysis**

The primary analysis population for immunogenicity will be the PP Set. Planned timepoints for all immunogenicity assessments are provided in the SoA available in Appendix A.

For Part 1, the following analytes will be measured:

- Influenza: Serum antibody level as measured by HAI assay and potentially serum neutralizing antibody (nAb) level as measured by microneutralization assay.
- SARS-CoV-2: Serum nAb titers as measured by pseudovirus neutralization assay (PsVNA) assay and potentially serum binding antibody titers by enzyme-linked immunosorbent assay or multiplex assay specific to the SARS-CoV-2 proteins.
- Cellular immunogenicity in a subset of participants.

For secondary and exploratory endpoints, the Geometric Mean Titer (GMT) will be calculated using the following formula (Nauta, 2011):

$$2^{\left\{ \frac{\sum_{i=1}^n \log_2(t_i)}{n} \right\}}$$

where  $t_1, t_2, \dots, t_n$  are  $n$  observed immunogenicity titers or levels.

The Geometric Mean Fold Rise (GMFR) measures the changes in immunogenicity titers or levels within participants. The GMFR will be calculated using the following formula:

$$2^{\left\{ \frac{\sum_{i=1}^n \log_2\left(\frac{v_{ij}}{v_{ik}}\right)}{n} \right\}} = 2^{\left\{ \frac{\sum_{i=1}^n \log_2(v_{ij}) - \log_2(v_{ik})}{n} \right\}}$$

where, for  $n$  participants,  $v_{ij}$  and  $v_{ik}$  are observed immunogenicity titers or levels for participant  $i$  at time points  $j$  and  $k$ ,  $j \neq k$ . For GMFR calculation, antibody values reported as below LLOQ will be replaced by LLOQ.

The 95% CIs for GMT and GMFR will be calculated based on the t distribution of the log-transformed values then back transformed to the original scale for presentation, unless otherwise specified.

#### 2.6.4.1. Secondary Immunogenicity Endpoints

- GMT and GMFR at Day 29 compared with Day 1 by HAI assay for influenza and PsVNA for SARS-CoV-2
- Influenza: Percentage of participants with seroconversion, defined as a Day 29 titer **CCI** if Baseline is **CCI** or a 4-fold or greater rise if Baseline is **CCI** in anti-HA antibodies measured by HAI assay

- SARS-CoV-2: Percentage of participants with seroresponse, defined as a Day 29 titer  $\geq 4$ -fold if Baseline is  $\geq$  LLOQ or  $\geq 4 \times$  LLOQ if Baseline titer is  $<$  LLOQ in nAb titers measured by PsVNA (or binding antibody assay)
- GMT and GMFR compared with Day 1 (Baseline) by HAI for influenza and PsVNA (or binding antibody assay) for SARS-CoV-2 at all evaluable timepoints
- Percentages of participants with seroconversion (influenza) and seroresponse (SARS-CoV-2) as defined below, at all evaluable timepoints

For the secondary immunogenicity endpoints, descriptive summaries statistics, including median, Q1, Q3, minimum, and maximum along with the number and percentage values above ( $\geq$ ) LLOQ and below ( $<$ ) LLOQ will be provided for the antibody titer values by treatment arm (available in Section 2.6.1) for the influenza and SARS-CoV-2 endpoints. In addition, the following endpoints summaries will be provided:

- Geometric mean of specific antibody titers (GMT) with corresponding 2-sided 95% CI at each time point
- Geometric mean fold rise (GMFR) of specific antibody titers with the corresponding 2-sided 95% CI at each post-Baseline time point over pre-injection Baseline at Day 1,

Listing presenting the antibody level, for each specific strain of influenza and SARS-CoV-2 will be provided. The ratio of post-Baseline/Baseline, LLOQ and ULOQ will be presented as well. An additional listing will be provided for participants with Influenza or SARS-CoV-2 infections.

Reverse Cumulative Distribution Function for each specific strain of influenza and SARS-CoV-2 will be provided. The box plot for GMT and GMFR will be provided at all evaluable timepoints. The bar plot for GMFR at Day 29 will also be provided.

$$2^{\left\{ \frac{\sum_{i=1}^n \log_2(t_i)}{n} \right\}} = 2^{\left\{ \frac{\sum_{i=1}^n \log_2(v_{ij}/v_{ik})}{n} \right\}} = 2^{\left\{ \frac{\sum_{i=1}^n \log_2(v_{ij}) - \log_2(v_{ik})}{n} \right\}}$$

Additional descriptions will be provided by treatment arm (available in Section 2.6.1) for the following influenza and SARS-CoV-2 endpoints:

- Percentages of participants with seroconversion (influenza) and seroresponse (SARS-CoV-2) with the corresponding 2-sided 95% CI at each post-Baseline time point,

- Percentages of participants with a GMFR results  $\geq 2$ , and  $\geq 4$  with the corresponding 2-sided 95% CI at each post-Baseline time point.

For participants in the groups receiving mRNA-1083, mRNA-1010 or influenza injections, seroconversion rate from Baseline will be provided with a 2-sided 95% CI using the Clopper-Pearson method at each post-Baseline time point. Rate of seroconversion is defined as the proportion of participants with either a pre-vaccination HAI titer CCI and a post-vaccination HAI titer CCI or a pre-vaccination HAI titer CCI and a minimum 4-fold rise in post-vaccination HAI antibody titer.

For participants in the groups receiving mRNA-1083, mRNA-1283.222 or mRNA-1273.222, seroresponse rate will be summarized for planned post-Baseline visits, including the 2-sided 95% CI using the Clopper-Pearson method. Rate of Seroreponse for SARS-CoV-2 is defined as a  $\geq 4$  fold rise in nAb titer from Baseline in those with Baseline titer  $\geq$  LLOQ, or a post-Baseline titer  $\geq 4 \times$  LLOQ if Baseline titer is  $<$  LLOQ.

In addition, the following analysis statistics will be provided by treatment arm (available in Table 7) at Day 29 and D181 for the following influenza and SARS-CoV-2 endpoints:

- Within Treatment Group, Model-based geometric mean titer (GMT) with the corresponding 95% CI,
- Between Treatment Group, Pair-wise geometric mean ratios (GMR) with the corresponding 95% CI

The model-based GM titer will be estimated based on an analysis of covariance (ANCOVA) model, and it will be modelled separately for Cohort A and Cohort B. In the ANCOVA model, the log-transformed antibody titer at a post-Baseline timepoint (Day 29 or Day 181) are treated as a dependent variable, with the treatment group as an explanatory variable and covariates listed in Table 6 below for different assays, Cohorts and subgroups:

